#### **3.5. Data Pooling**

Data from all sites will be pooled together for all analyses.

#### **3.6. Handling of Missing Data**

No missing data imputation will be performed. For efficacy variables, if any item is missing, the subscale and summary score will be set to missing.

## 4. STUDY SUBJECTS AND EXPOSURE

#### 4.1. Subjects Disposition

Subject disposition will be summarized descriptively by the optimized dose group and overall including the following categories:

- Number of subjects enrolled.
- Number of subjects in the Safety population
- Number (%) of subject who completed the study
- Number (%) of subjects who discontinued from the study
- Primary reasons of discontinuation may include any of the following:
  - Withdrawal by subject
  - Withdrawal by parent/guardian
  - Lost to follow-up
  - Adverse event
  - Physician decision
  - Lack of efficacy
  - Protocol violation
  - o Other

#### 4.2. Protocol Deviations

A protocol deviation is defined as any change, divergence, or departure from the study design or procedures defined in the protocol. An important protocol deviation (IPD) is defined as a protocol deviation that might significantly affect the completeness, accuracy, and/or reliability of the study data or that might significantly affect a subject's rights, safety, or well-being.

Potential IPDs may include, but are not limited to:

- Non-compliance with any scheduled study visit
- Non-compliance with study treatment
- Disallowed concomitant medications
- Non-compliance with study inclusion or exclusion criteria
- Non-compliance with study assessment procedures

IPDs will be provided in subject data listings.

SPN-810

# 4.3. Demographic and Baseline Characteristics

The summaries of demographic data and baseline characteristics will be provided for the Safety Populations. Subject demographic data (age, sex, race, and ethnicity) will be summarized descriptively by the optimized dose group and overall.

# 4.4. Medical History

Medical history will be coded using the Medical Dictionary for Regulatory Activities MedDRA version 18.1. The number and percent of subjects reporting various medical, family, and psychiatric histories, grouped by system organ class (SOC) and preferred term (PT), will be summarized for the Safety Population descriptively by the optimized dose group and overall.

# 4.5. Prior and Concomitant Medication

Prior and Concomitant medications will be coded using WHO DRUG Global version March 2019, and will be summarized descriptively by the fourth level anatomical therapeutic chemical (ATC) classification and Preferred Name (PN), using counts and percentages for the Safety Population by the optimized dose group and overall. ATC fourth (ACT4) level is for the chemical, pharmacological or therapeutic subgroup.

# 4.6. Study Treatment Exposure and Compliance

Duration of treatment exposure will be calculated for each subject by taking the difference between the date of last dose minus the date of baseline, plus 1 (date of last dose – date of baseline +1). Duration of treatment exposure will be summarized descriptively by the optimized dose group and overall.

Duration of treatment exposure will also be summarized by duration category (i.e., 0 to <3, 3 to <6, 6 to <9, 9 to <12, 12 to <15, 15 to <18, 18 to <21 21 to < 24, 24 to < 30, 30 to <36, 36 to <42, 42 to <48, 48 to <54, 54 to < 60,  $\geq$  60 months) using descriptive statistics.

Percentage compliance will be calculated as the following:

$$\left(\frac{\sum_{i=start\ visit^{-1}}^{last\ visit^{-1}}(Dose\ in\ mg\ dispensed\ at\ visit_{i}-Dose\ in\ mg\ returned\ at\ visit_{i+1})}{\left(\sum_{i=start\ visit}^{last\ visit^{-1}}(Y_{i}\ \times \#\ of\ days\ from\ visit_{i}\ to\ visit_{i+1})\right)}\right)\times 100$$

Where *i*=index of visits within a given period (e.g., titration, maintenance, and overall);  $Y_i$ = Dose in mg that the subject was instructed to take daily between visits.

Descriptive statistics for SM compliance along with the number and percent of subjects belonging to compliance categories (<80%, 80-120%, and >120%) will be provided.

SPN-810

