4.2.8 Visit 25 [(End of Study (EOS)] (Month 60 +/- 2 weeks)

Subjects who complete the study (60 months) will be instructed to down titrate for 2 weeks before returning to the office for the EOS Visit.

This document is confidential. It contains proprietary information of Supernus® Pharmaceuticals, Inc. Any viewing or disclosure of such information that is not authorized in writing by the Sponsor is strictly prohibited. Such information may be used solely for the purpose of reviewing or performing this study.

Subjects may discontinue prior the end of the study if the subject or the LAR withdraws assent and/or consent, or if the Investigator or the Sponsor decide it is no longer in the best interest of the subject. If the decision is made to discontinue early then the subject will be contacted and instructed to down-titrate at least 2 weeks prior to the EOS Visit.

The following procedures will be performed for subjects who complete the study (60 months) or discontinue early.

1. Perform physical examination
2. Perform 12-lead ECG
3. Collect urine sample for urinalysis and urine drug screen (all subjects), and pregnancy test (FOCBP only)
4. Record vital signs (HR, BP, temperature, and RR)
5. Record height, weight and BMI
6. Collect blood samples for hematology and chemistry
7. Administer C-SSRS
8. Administer safety scales (Simpson-Angus, Barnes Akathisia, AIMS)
9. Administer efficacy scales (R-MOAS, CGI-I and CGI-S, only for subjects who discontinue early)
10. Administer quality life scales (CHQ-PF28, PSI-4-SF or SIPA, only for subjects who discontinue early)
11. Collect and assess adverse events
12. Collect SM and assess treatment compliance
13. Assess and record concomitant medications

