4.6 Completion of Study and Discontinuation of Subjects

Subjects will be considered to have completed the study if they complete all visits up to and including the end of study visit. All subjects who discontinue early will be contacted by the study staff and instructed to down-titrate gradually over approximately 2 weeks prior to the EOS visit.

The Investigator(s) or subjects themselves may stop SM treatment at any time for safety or personal reasons. A subject is free to withdraw from the study at any time for any reason without prejudice to their future medical care by the physician or at the institution. The Investigator or Sponsor may also withdraw the subject at any time in the interest of subject safety. The withdrawal of a subject from the study should be discussed where possible with the Medical Monitor and/or the Investigator before the subject stops SM. Subjects removed from the study for any reason will not be replaced.

Reasons for withdrawal may include but are not limited to subject withdrawal of consent, occurrence of unmanageable AEs, or at the Investigator's discretion.

The primary reason for withdrawal must be recorded in the subject's medical record and on the eCRF. If a subject is withdrawn for more than one reason, each reason should be documented in the source document and the most medically significant reason should be entered on the eCRF.

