6.7 Study Medication Exposure and Compliance

Duration of exposure is defined as the total number of days a subject is exposed to study treatment. This will be calculated for each subject by taking the difference between the date of last dose *minus* the date of the first dose, *plus* one (date of last dose – date of first dose +1).

Duration of Treatment exposure will also be summarized using descriptive statistics (n, mean, SD, median, minimum, and maximum).

Percent of study drug compliance will be calculated as

$\{(D-R)/(T*(D_L - D_F +1))\} * 100$, where D=number of tablets dispensed, R= number of tablets returned, T= number of tablets administered per day, D_L = date of last visit (dose) and D_F = date of first visit (dose)

The number of tablets (T) taken each day may vary during the maintenance phase: subjects can take up six tablets per day to the maximum dose of 54mg/day BID.

The study medication compliance will be summarized by compliance category (<80%, 80-120%, and >120%) and number of subjects in each compliance category. Study medication compliance will also be summarized as a continuous variable using descriptive statistics (n, mean, standard deviation, median, minimum, and maximum).

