# 8. CHANGE FROM THE PROTOCL

Drug compliance in section 4.6 calculation was changed to use dose in mg instead of tablet because different tablet (ie. tablet) could be distributed in the same visit and

patient can take them interchangeably.

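### The SAP 4.6 compliance denominator runs visit to visit at one instructed dose and does not stop at the last dose, so compliance is biased downward for adherent subjects who leave between visits

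*SAP*

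**What the plan says.** SAP 4.6 computes percentage compliance as milligrams dispensed minus milligrams returned, divided by the sum over visit intervals of Y_i times the days from one visit to the next. Y_i is the "Dose in mg that the subject was instructed to take daily between visits". The sum ends at the last visit. The calculation is made within periods ("e.g., titration, maintenance, and overall"); taper is not among the examples. Results are shown as descriptive statistics and in three bands: "compliance categories (<80%, 80-120%, and >120%) will be provided".

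The same SAP section ends duration of exposure at the date of last dose, so exposure and compliance cover different days for the same subject.

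Protocol 6.7 counted tablets over a span ending at the "date of last visit (dose)". SAP 8 states that "Drug compliance in section 4.6 calculation was changed to use dose in mg instead of tablet" and declares no other change to the calculation.

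On leaving the study, Protocol 4.2.8 says that an early leaver is contacted and "instructed to down-titrate at least 2 weeks prior to the EOS Visit". Protocol 4.6 has a similar instruction, with the length given as approximate. It also says that investigators or subjects "may stop SM treatment at any time for safety or personal reasons". Study drug is collected and compliance assessed at the EOS visit, so the interval ending there can enter the formula.

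**The concern.** An early leaver is contacted and told to down-titrate, and this can happen between scheduled visits. The final interval may then hold days at the previous dose, days on a falling dose and days on no drug. One Y_i cannot describe such an interval.

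If unused tablets are returned, the numerator falls as it should. The denominator keeps counting every calendar day to EOS. Days after the last dose are charged at whatever nonzero Y_i is entered. Taper days are charged too much if the programmer enters the pre-taper dose, which the SAP neither requires nor rules out. The gradual titration of washed-out entrants (Protocol 3.2.1) raises the same difficulty of one dose per interval.

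The error goes in one direction and is largest, as a share of the total, for subjects with little time on drug. At stake is whether some short-stay subjects who followed every instruction appear in the band below 80%, and whether the compliance summary can be read alongside the exposure summary.

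**Working it through.** The plan gives no worked compliance value, so there is no figure to reproduce. The check applies the SAP 4.6 formula to a subject who takes every instructed dose and returns every unused tablet.

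**Inputs from the documents**
- One Y_i per interval, with calendar days counted to the last visit (SAP 4.6).
- Band limit of 80% (SAP 4.6).
- Taper of about 2 weeks before EOS (Protocol 3.2.5, 4.2.8, 4.6), taken here as 14 days.

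**Assumptions, not in the documents**
- f, the mean taper dose as a fraction of the prior dose: 0.33, 0.50 and 0.67.
- g, the off-drug days before EOS: 0 or 14.
- Y_i is the pre-taper dose during the final interval.
- d is the number of days at a constant pre-taper dose.

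**Formulas, overall period**
- With taper: compliance = 100 × (d + 14f) / (d + 14 + g).
- With taper, below 80% when d < [0.8 × (14 + g) − 14f] / 0.2.
- Immediate stop: compliance = 100 × d / (d + g), below 80% when d < 0.8g / 0.2 = 4g.

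Check: with no taper and g = 0 the result is 100%.

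**Cut-offs for falling below 80%**
- Taper, g = 0, f = 0.33: (11.2 − 4.62) / 0.2 = 32.9 days.
- Taper, g = 0, f = 0.50: (11.2 − 7.0) / 0.2 = 21 days.
- Taper, g = 0, f = 0.67: (11.2 − 9.38) / 0.2 = 9.1 days.
- Immediate stop, g = 14: 4 × 14 = 56 days.
- Taper followed by a 14-day gap, f = 0.50: (22.4 − 7.0) / 0.2 = 77 days.

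**Compliance (%) of a fully adherent subject**

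| Case | d = 14 | d = 28 | d = 56 | d = 84 | d = 180 |
|---|---|---|---|---|---|
| Taper, f = 0.50, g = 0 | 75.0 | 83.3 | 90.0 | 92.9 | 96.4 |
| Taper, f = 0.50, g = 14 | 50.0 | 62.5 | 75.0 | 81.2 | 89.9 |
| Immediate stop, g = 14 | 50.0 | 66.7 | 80.0 | 85.7 | 92.8 |

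At d = 175:
- Taper, f = 0.50, g = 0: (175 + 7) / 189 = 96.3%, about 4 points low.
- Immediate stop, g = 14: 175 / 189 = 92.6%, about 7 points low.

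**In milligrams (illustration only).** Take 14 days at 36 mg/day, then 14 taper days averaging 18 mg/day, with g = 0. Used: 504 + 252 = 756 mg.
- Taper days charged at the pre-taper dose: 36 × 28 = 1008 mg, so 756 / 1008 = 75%.
- Taper days charged at the instructed dose: 504 + 252 = 756 mg, so 100%.
- Taper days charged at the instructed average, but EOS 7 days after the last dose: 504 + 18 × 21 = 882 mg, so 756 / 882 = 85.7%.

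The last line shows that the missing stop at the last dose matters even when the taper itself is charged correctly.

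**By period.** If the maintenance period is taken to run to EOS, earlier treatment does not dilute the error. A subject who starts taper 14 days after maintenance begins scores 75% for maintenance (f = 0.50, g = 0) whatever happened before. The SAP does not say whether that interval belongs to maintenance.

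**The case against.** The strongest reply is that Y_i is the instructed dose. During taper the instructed dose is the taper dose, so nothing in the SAP says that taper days are charged in full. At Visit 6 and later even-numbered visits, taper drug and instructions can be dispensed (Protocol 4.2.6, 4.2.7 and Table 1). Those subjects have a separate taper interval, which can score 100% if EOS falls at the last dose. This stands. A reader might infer that the SAP always charges a full dose during taper, but the text supports only that Y_i is undefined when the dose changes within an interval.

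A reader might also infer that adherent early leavers in general are scored as non-compliant. The figures above do not support that: under the taper assumptions with g = 0, nobody with 33 or more pre-taper days falls below 80%. The documents give no taper steps, no distribution of leaving times and no time from an immediate stop to EOS, and Protocol 3.2.5 says that all early leavers taper. The immediate stop with a 14-day gap is therefore a constructed case, and no share of leavers affected can be stated. A share taken over Days 7-56, for instance, would put nearly all immediate stoppers below 80% only because the window ends at the cut-off.

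Three further inferences also lack support.
- **Undeclared change of end date.** The protocol's wording is ambiguous between visit and dose and names the visit first, so it does not show that the SAP moved the end date.
- **False protocol deviations.** SAP 4.2 lists treatment non-compliance as a potential important deviation, but nothing links it to this formula or to the 80% limit.
- **Treatment failures made to look non-adherent.** No planned table crosses compliance with reason for discontinuation.

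The reply does not remove the main point. The denominator has no stop at the last dose, although the same section uses one for exposure. A taper that starts between visits has no defined Y_i.

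**Conclusion.** The point holds in a limited form. As written, SAP 4.6 charges off-drug days before EOS at any nonzero Y_i and cannot represent a dose that changes within an interval. For adherent subjects who leave between scheduled visits the bias is downward.

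A change of band is confined to short stays: the 9-33 day cut-off with a taper and the 56-day cut-off with an immediate stop rest on the assumed taper fraction, the assumed gap and Y_i being the pre-taper dose. A gap after the taper lengthens the range (77 days for a half-dose taper and a 14-day gap). Later leavers usually keep their band. A 60-month completer is hardly touched: about 99.6% overall, from (1825 + 7) / 1839, with f = 0.50 and g = 0.

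The damage is limited to the descriptive compliance table. Compliance defines no analysis population, since the Safety Population serves all analyses, and no safety or efficacy table changes. This is a minor point, worth correcting because the correction is cheap.

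**What to change.** In SAP 4.6:
1. End the denominator at the date of last dose, as the section already does for exposure.
2. Replace Y_i times days with the sum, over calendar days, of the milligrams instructed for that day, so that within-interval changes and taper days count at the instructed dose. A fully adherent leaver then scores 100% whatever d, f and g are.
3. If dated taper doses are not recorded, end the compliance calculation on the day before taper starts and remove taper-period drug from the numerator.
4. State which period the taper/EOS interval belongs to.
5. List the change in SAP 8 beside the change from tablets to milligrams.

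Stopping at the last dose alone is not enough if taper days are still charged at the pre-taper dose: with f = 0.50, d = 14 would still score 75.0% and d = 28 would score 83.3%.

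The cost is a few sentences and minor programming, with reliance on recorded dosing dates. The documents do not show that daily instructed doses during taper are collected, which is why item 3 is needed as a fallback. No clinical procedure changes.

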## 5. SAFETY ANALYSES

The assessment of overall safety and tolerability will be based on adverse events, laboratory values, vital signs, body size (Height/Weight/BMI), ECGs, physical examinations, Barnes Akathisia Scale, Barnes Akathisia Scale, Abnormal Involuntary Movement Scale (AIMS), and Columbia Suicide Severity Rating Scale (C-SSRS).

## 5.1. Adverse Events

All adverse events (AEs) will be coded using the MedDRA Version 18.1. All AEs reported in this study are considered treatment-emergent adverse events (TEAEs).

The incidence of TEAEs (number and percent of subjects) will be summarized by System Organ Class (SOC), preferred term (PT), and by the optimized dose group and overall. A subject with multiple occurrences of an AE will be counted only once in the AE category per SOC and PT for summary tables.

Based on the investigator's determination, the severity of TEAEs will be classified as mild, moderate or severe. For summaries by severity, a patient experiencing multiple AE in the same preferred term with different intensities will only be counted once with the maximum severity. If severity is missing, then the maximum severity will be assumed for the analysis (i.e., severity = severe).

The relationship between the study medication and a TEAE is determined by the investigator and will be classified as unrelated (i.e., unlikely related and not related) or related (possibly related and definitely related). TEAEs with missing relatedness will be counted as definitely related. For summaries by relationship, a patient experiencing multiple AE in the same preferred term with different relationship will only be counted once with the most related occurrence.

The summary of TEAE will include incidence rates (number and percent of subjects) who had at least one TEAE, treatment related TEAE, serious TEAE, TEAE leading to death, TEAE by maximum severity, treatment related TEAE, treatment related SAE, and TEAE of special interest.

In addition to the overview of TEAE summary, the following TEAE summary tables will be provided:

- Number and Percent of Subjects with Treatment-Emergent Adverse Events by System Organ Class and Preferred Term
- Number and Percent of Subjects with Common (≥ 5% in Any Treatment Group) Treatment-Emergent Adverse Events by Preferred Term
- Number and Percent of Subjects with Treatment-Emergent Adverse Events by System Organ Class, Preferred Term, and Severity

- Number and Percent of Subjects with Treatment-Emergent Adverse Events by System Organ Class, Preferred Term, and Relationship to Study Medication
- Number and Percent of Subjects with Serious Treatment-Emergent Adverse Events by System Organ Class and Preferred Term
- Number and Percent of subjects with Treatment-Emergent Adverse Events Leading to Withdrawal of Study Medication by System Organ Class and Preferred Term
- Number and Percent of Subjects with Treatment-Emergent Adverse Events of special interest by System Organ Class and Preferred Term *Note: Adverse events of special interest (AESI) are collected and flagged on eCRF.*
- Listing of Deaths

A data listing of death will be provided. If no death occurred, a blank listing with "No subject died on this study." will be presented.

Listing will be provided for AEs.

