1.5 Study Rationale

Results from Phase 2 studies and the associated open label study have shown that molindone hydrochloride extended-release (SPN-810) is safe and well tolerated in the target population of children 6-12 years of age. The goal of the phase 3 studies is to support the efficacy, safety and tolerability of SPN-810 in reducing the frequency of IA behaviors. This Phase 3 study, 810P304, is available to eligible subjects who complete the randomized, double-blind portion of one of the three Phase 3 studies, 810P301, 810P302, 810P503 or the additional Phase 2 study, 810P204. Subjects who discontinue during the maintenance phase may be allowed to participate in the OLE on a case-by-case basis only after consultation between the Investigator, the Medical Monitor and the Sponsor.

The objective of this extension study is to collect additional long-term safety data on the use of SPN-810 for the treatment of IA in subjects diagnosed with ADHD in conjunction with a standard ADHD treatment (stimulant or non-stimulant) and to collect additional data on the maintenance of the effect on IA behaviors and quality of life.

Monitoring the occurrence of any treatment emergent AEs, concomitant medications and the frequency of extrapyramidal symptoms are the primary outcome measures for this study.

In addition to safety, we will assess the severity of aggressive behaviors using the R-MOAS scale, and the severity and improvement of IA using the CGI scales. Changes in CHQ-PF28 and PSI-4-SF or SIPA scores will be used to evaluate improvement of quality of life of both the subject and the caregiver.

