5.1.3.2 Other Events Requiring Immediate Reporting

The Investigator must report a **pregnancy** that occurs in a subject during a clinical study to the Drug Safety Contact within 24 hours of first becoming aware of the event. Pregnancy should be reported on a Pregnancy Report Form. The Investigator should discuss the case with the Medical Monitor also, he/she must follow any pregnant subject for 3 months after the child is born. The Investigator must complete a Pregnancy Outcome Form as follow up. Any AEs concerning the pregnancy of the subject during pregnancy or the child after birth must be documented and reported to the Sponsor.

Treatment-emergent **extrapyramidal symptoms** (e.g. akathisia, dystonia, Parkinsonism, tardive dyskinesia) and neuroleptic malignant syndrome should be reported to the Drug Safety Contact person(s) by completing the Adverse Event Special Interest (AESI) eCRF in EDC. Should the site be unable to access EDC, a paper AESI form must be completed and sent to [REDACTED] Drug Safety by email or fax within 24 hours of first becoming aware of the event. Once EDC becomes available, the site must complete the AESI eCRF in EDC. EPS incidence will be summarized and shared with study Investigators throughout the clinical trial.

Overdosage of molindone presumably may be manifested by severe EPS and sedation. Coma with respiratory depression and severe hypotension resulting in a shock-like syndrome could occur. In the

event of a suspected overdose, the parent or LAR should be instructed to call 911 or their local poison control center at [name].

Symptomatic, supportive therapy should be the rule. Gastric lavage is indicated for the reduction of absorption of molindone which is freely soluble in water. Since the adsorption of molindone by activated charcoal has not been determined, the use of this antidote must be considered of theoretical value.

Emesis in a comatose patient is contraindicated. Additionally, while the emetic effect of apomorphine is blocked by molindone in animals, this blocking effect has not been determined in humans.

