5.1.4 Management of Treatment-Emergent EPS

If a subject experiences treatment-emergent EPS (including akathisia, dystonia, Parkinsonism, or tardive dyskinesia), benztropine will be permitted at a starting dose of 0.5 mg BID up to a range of 1 to 4 mg/day. Lorazepam (1 to 2 mg per dose not to exceed three times daily) and clonazepam (0.25 to 1 mg per dose not to exceed twice daily) will also be permitted to treat the occurrence of extrapyramidal symptoms.

For the treatment of Akathisia, propranolol is recommended up to 90 mg /day in divided doses, three times per day, starting at 10 mg BID and up to 30 mg TID, as needed.

A positive finding on an EPS safety assessment scale (Barnes Akathisia, Simpson-Angus, AIMS) does not necessarily equate to an EPS event. Investigators should evaluate positive findings on the EPS safety assessment scales and integrate them into a global clinical observation to determine if an AE of EPS should be recorded.

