6.8.1 Adverse Events

AEs will be classified into standardized medical terminology from the verbatim description (Investigator term) using the Medical Dictionary for Regulatory Activities (MedDRA). AEs will be summarized using discrete summaries at the subject and event level by system organ class and preferred term for each group of doses. Similarly, treatment-emergent AEs will be summarized by severity and relationship separately. Verbatim description and all MedDRA level terms, including the lower level terms, for all AEs will be contained in the subject data listings.

All AEs occurring throughout the study period will be recorded. Treatment-emergent AEs (TEAEs) will be collected starting after the first dose of SM (Visit 1) to the end of the study. These AEs include those that emerge during treatment or worsen in severity during treatment. These AEs will be tabulated, listed and analyzed.

TEAE incidence tables will be listed and summarized by the group of the optimized doses (<18 mg/day; 18-24 mg/day, 24-36 mg/day or 36-54 mg/day) the subject received. The incidence rates for all SADRs will also be summarized as described for all TEAEs.

Listings (and tabular summaries, if warranted) of deaths, other SAEs, and other significant TEAEs, including TEAEs resulting in treatment discontinuation, will be provided.

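### The SAP's only grouped count of EPS adverse events depends on an eCRF flag, also takes in neuroleptic malignant syndrome, and has no term-based check

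*SAP*

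**What the plan says.** Protocol 1.5 (Study Rationale) states: "Monitoring the occurrence of any treatment emergent AEs, concomitant medications and the frequency of extrapyramidal symptoms are the primary outcome measures for this study".

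Protocol 5.1.3.2 sends treatment-emergent EPS, with four diagnoses given as examples, and neuroleptic malignant syndrome to Drug Safety on a dedicated AESI form in the eCRF. It also promises that EPS incidence will be summarized for investigators while the trial runs. Protocol 5.1.4 says of the rating scales: "Investigators should evaluate positive findings on the EPS safety assessment scales and integrate them into a global clinical observation". The investigator then decides whether an EPS adverse event is recorded.

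On analysis, protocol 6.8.1 says "AEs will be summarized using discrete summaries at the subject and event level by system organ class and preferred term". Protocol 6.8.8 adds, for every item of the three EPS scales, how many subjects and what share scored worse than baseline at some later visit.

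SAP 5.1 plans the table "Number and Percent of Subjects with Treatment-Emergent Adverse Events of special interest by System Organ Class and Preferred Term", with the note "Adverse events of special interest (AESI) are collected and flagged on eCRF", and an overview row for TEAEs of special interest. It separately plans "Number and Percent of Subjects with Treatment-Emergent Adverse Events by System Organ Class and Preferred Term", tables by severity and by relationship, a table of common TEAEs (at least 5% in any group), and an adverse event listing. Subjects are counted once per SOC and PT. SAP 5.6 summarizes item values and change from baseline on the EPS scales by visit. SAP section 8 declares one change from the protocol, the compliance formula.

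**The concern.** A frequency of EPS needs a numerator: subjects with at least one EPS event. The SAP never defines that numerator by coded terms. The only grouped figure it will produce is whatever was entered as AESI, and that category is not EPS alone. Sites may record tremor, rigidity or restlessness as an ordinary adverse event without the AESI entry. Those subjects are then absent from the grouped count, and nothing in the plan would reveal it.

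At stake is a safety figure that the protocol itself singles out, for a D2 antagonist given to children and adolescents for up to 60 months. The sponsor reported the same kind of grouped figure for its earlier extension, study 810P203, so readers will look for one here. Without a fixed definition, the figure depends on site practice across about 50 centers, or on a term list chosen after the data are seen.

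**Working it through.** **1. The only EPS rate in the documents.** Protocol 1.3 gives n=2, 2.6%, for EPS-associated adverse events in study 810P203, where 78 subjects continued into the extension. 2/78 = 0.0256 = 2.56%, which rounds to the stated 2.6%. The exact 95% interval is 0.3% to 9.0%. This is background. It shows only that EPS counts can be small.

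**2. Which planned output gives the number of subjects with any EPS event?**

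| Output | Uses the flag? | Subjects with at least one EPS event? |
|---|---|---|
| AESI overview row (SAP 5.1) | Yes | Only if every EPS event is flagged; also counts neuroleptic malignant syndrome |
| AESI table by SOC and PT (SAP 5.1) | Yes | Same limit; neuroleptic malignant syndrome has its own PT row |
| All TEAEs by SOC and PT; by severity; by relationship (SAP 5.1) | No | No, separate PT rows |
| Common TEAEs (SAP 5.1) | No | No; with overall EPS near 2.6%, single EPS terms may not reach 5% |
| Adverse event listing (SAP 5.1) | No | No count |
| EPS scales by visit (SAP 5.6) | No | No, item values and changes only |

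**3. Why PT rows cannot be added.** Let n_k be the number of subjects in the row for EPS term k, and N_any the number with at least one EPS term. A subject with two terms sits in two rows, so the table fixes only bounds:

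max(n_k) ≤ N_any ≤ Σ n_k

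A hypothetical case with the 810P203 denominator: two rows of one subject each fit either one subject (1/78 = 1.3%) or two (2/78 = 2.6%). The table cannot tell them apart.

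**4. Why the SOC row is no substitute.** In 810P203, nervous system disorders ran at 8.7% to 15.5% by dose group, against 2.6% overall for EPS. The class is far wider than EPS.

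**5. Protocol against SAP.**

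| Protocol promises | SAP plans | In SAP section 8? |
|---|---|---|
| 6.8.1: subject-level and event-level summaries | 5.1: subject counts only | No |
| 6.8.8: subjects worse than baseline at some later visit, per item | 5.6: item values and change from baseline by visit | No |

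Visit-by-visit summaries do not yield the 6.8.8 figure. A subject who worsens at several visits appears in each, so visits cannot be added any more than PT rows can. Without event counts, recurrent EPS under one term looks like a single episode in every table.

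**6. Direction and size.** Let E be the number of subjects with EPS, s the share of them with a flagged event, and X the subjects whose only AESI entry is neuroleptic malignant syndrome or a mis-flagged event. The overview row shows

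A = s × E + X

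Neither s nor X is given. A falls below E when X < (1 − s) × E and exceeds it when X > (1 − s) × E. Neither the size nor the sign of the error can be derived from the documents.

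**The case against.** The best defence is that nothing is lost from the record. All adverse events are coded, all count as treatment-emergent, and the SOC/PT, severity and relationship tables and the listing ignore the flag. A reader might infer that unflagged EPS events are omitted from the analysis. The documents do not support that: what is missing is the grouped subject count. This part of the defence stands.

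A reader might also infer that the grouped figure can only be too low. It cannot be put so strongly, because neuroleptic malignant syndrome or over-flagging can raise the overview total. In the AESI table itself that syndrome has its own row.

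Nor is the flag shown to be a casual tick-box. Protocol 5.1.3.2 directs EPS as a class to a dedicated form, with a paper back-up, and nothing shows that this route fails. Protocol 5.1.4 concerns whether a scale finding becomes an adverse event at all, not whether a recorded one is flagged. A term-based count would not recover events that were never recorded.

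Finally, SAP Table 1 lists the three EPS scales as a safety endpoint of their own, they are rated at every visit, and neither document names the AESI table as the EPS outcome. That is fair. It would answer the point if the scales supplied a frequency, but the SAP has dropped the one in protocol 6.8.8. Even that one was per item, not a count of subjects with any EPS event.

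**Conclusion.** The gap is real but limited. A measure named in protocol 1.5 has no pre-specified, flag-independent subject count in the SAP, and two protocol summaries that would have helped are gone without being declared. This rests on the text alone. It assumes that the SAP's AESI are the events assigned to the AESI form in protocol 5.1.3.2, since the SAP gives no definition of its own.

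No number can be put on the miscount. It is tempting to divide 2.6% by an assumed flagging sensitivity. Nothing says the 810P203 figure was flag-based, that study ran for up to 6 months against up to 60 here, and the documents give no flagging completeness. The change should be made because it is cheap and bears on a key safety figure, not because an error has been shown.

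**What to change.** In SAP 5.1:

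- Pre-specify an EPS term list, for example the MedDRA extrapyramidal syndrome SMQ, narrow and broad. A fixed sponsor list would also serve. Apply it to all coded TEAEs regardless of the flag.
- Tabulate subjects with any EPS term and the number of events, by optimized dose group and overall.
- Show neuroleptic malignant syndrome separately.
- Keep the AESI table and reconcile it with the term-based count, showing events found by one route and not the other.

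In SAP 5.6, restore the worsening table of protocol 6.8.8, or declare its removal in section 8. Likewise restore the event-level adverse event summary of protocol 6.8.1 or declare the change.

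The cost is SAP text and one or two tables from data already coded, with no new collection. The EPS rate may come out less favourable, and a broad list brings in some non-specific terms, which is the reason to show narrow and broad side by side.
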